8.4.4.5.1. Data Submission

Once required testing has been performed, complete and submit the appropriate forms to Abbott. Refer to **Table 4: Subject visit data collection summary**.

Upload the pre-MRI scan device session records through the EDC study portal. It is recommended that the following device printouts and measurements be maintained at the site.

- FastPath Summary
- Test Results with Freezes, Include Battery & Leads
- Wrap-up Overview with full parameters
- Device MRI summary report

8.4.4.6. Post MRI scan testing

Device Assessment and Programming

Following the MRI Scan, remove the subject from the MRI bore. Interrogate the ICD/CRT-D. Disable the MRI Settings. **Note: MRI settings must be disabled to ensure that tachyarrhythmia therapy is turned back on.** Obtain the following for the study leads: Interrogate the ICD/ CRT-D, and obtain the following for the Study leads:

- In-clinic bipolar and unipolar* capture threshold at a pulse width of 0.5 ms. Either the manual decrement or automatic (in-clinic, programmer-based) method may be used to obtain the capture threshold.
- In-clinic bipolar sensing amplitude. Either the incremental or the automatic (in-clinic, programmer based) method may be used to obtain the sensing threshold.
- In-clinic atrial and ventricular bipolar and unipolar* lead impedance

**NOTE: Unipolar and bipolar configurations should be collected for LV leads*

***NOTE:** RV capture thresholds are not required to be obtained if a high ventricular rate is present. If available, sites should use the automatically obtained pacing capture threshold from the most recent archival data as a substitute for the in-clinic capture threshold. RV sensing measurements are not required if the subject's intrinsic rate is established to be ≤ 30 beats per minute.*

Reporting of MRI Scan-Related Adverse Events

An ADE or SADE related to the following should be reported as soon as possible, but no later than 24 hours after the site becomes aware of the event, to Abbott: clotting, pulmonary embolism, or heating of the device pocket during the MRI scan. These events are likely to be associated with symptoms occurring during or immediately following the MRI scan and may manifest as chest pain, shortness of breath, or changes in vital signs during or immediately following the MRI scan.

To ensure all ADEs or SADEs related to or caused by the MRI scan are appropriately captured, before starting the scan, verbally instruct the subject to report symptoms of chest

pain, shortness of breath or pocket discomfort that he/she experiences while being scanned or immediately after exiting the scanner. Note changes in vital signs such as changes in heart rate, room air blood oxygen saturation, and/or respiration rate that occur during the MRI scan that may suggest an ADE or SADE has occurred due to clotting, pulmonary embolus or related to lead tip or device pocket heating.

If symptoms during or immediately after the MRI scan suggest that an ADE or SADE has occurred due to clotting, pulmonary embolus or related to lead tip or device pocket heating, test to assess possible causes. Diagnostic testing may be performed in any order deemed appropriate by the investigator; if any test was not performed, provide medical justification for not performing that test:

- (1) A 12 lead ECG
- (2) A 2-view chest X-ray (PA and Lateral)
- (3) Room air Oxygen saturation
- (4) A transthoracic echocardiogram

If the subject reports pocket discomfort, ask the subject for additional descriptive information and determine if the pocket is discolored or warm to the touch. ECG, chest x-ray, room air blood oxygen saturation, or transthoracic echocardiogram testing are not required to be performed for symptoms related to device pocket heating.

Sites should report an ADE or SADE if the subject experiences a significant rise in pacing threshold ([contact] or greater) from pre-MRI scan to one-month post-MRI scan.

8.4.4.6.1. Data submission

Once required testing has been performed, complete and submit the appropriate forms to Abbott. Refer to **Table 4: Subject visit data collection summary**.

Export the study MRI scan onto a CD, or other form of electronic media in DICOM format, and send to Abbott. Upload post MRI scan device session records through the EDC study portal. It is recommended that the following device printouts and measurements be maintained at the site:

- FastPath Summary
- Test Results with Freezes, Include Battery & Leads
- Wrap-up Overview with full parameters
- Device MRI summary report

8.4.4.7. One (1) month post scan visit

8.4.4.7.1. Testing

Interrogate the ICD/ CRT-D and obtain electrical lead measurements.

- In-clinic bipolar and unipolar* capture threshold at a pulse width of 0.5 ms. Either the manual decrement or automatic (in-clinic, programmer based) method may be used to obtain the capture threshold. If a significant rise in pacing threshold ([contact] or greater) from pre-MRI scan to one-month post MRI scan has occurred, then complete an AE form.
- In-clinic bipolar sensing amplitude. Either the incremental or the automatic (in-clinic, programmer based) method may be used to obtain the sensing threshold.
- In-clinic atrial and ventricular bipolar and unipolar* lead impedance
- Evaluate the subject for ADE and SADE and submit an AE CRF- if applicable.

***NOTE:** *Unipolar and bipolar configurations should be collected for LV leads*

NOTE: *RV capture thresholds are not required to be obtained if a high ventricular rate (e.g. 110bpm) is present. If available, sites should use the automatically obtained pacing capture threshold from the most recent archival data as a substitute for the in-clinic capture threshold. RV sensing measurements are not required if the subject's intrinsic rate is established to be ≤ 30 beats per minute.*

8.4.4.7.2. Data submission

Once required testing has been performed, complete and submit the appropriate forms to Abbott. Refer to **Table 4: Subject visit data collection summary**.

It is recommended that the following device printouts and measurements be maintained at the site.

- FastPath Summary
- Test Results with Freezes, Include Battery & Leads
- Wrap-up Overview with full parameters
- Device MRI summary report

If an ADE or SADE events has occurred, submit an AE CRF (as applicable). Report withdrawal and out of service as applicable. Upload device session records through the EDC study site portal (as applicable).

8.4.5. Situations where subject does not meet enrollment criteria

If a subject does not meet all inclusion criteria or meets any of the exclusion criteria, the subject cannot participate in the study and cannot be enrolled.

In case the subject was already consented to participate in the study, but did not meet inclusion/exclusion criteria, the following actions will be taken (**Table 7**). The EC/IRB should be notified of deviations according to each respective entity's guidelines.

TABLE 7: ACTIONS FOR INCLUSION/EXCLUSION CRITERIA ISSUES OCCURRING POST CONSENT

Issues where patient was consented, but did not meet inclusion/exclusion criteria	Action
If the subject did not have a successful implant procedure or successful re-attempt to implant with the study devices	
 • Document consenting information (name of the study, date of consent and inclusion/exclusion) in the subject's medical and/or study records • Complete the withdrawal CRF. The subject is withdrawn.
If the MRI Pre-Scan Visit has taken place, the MRI Settings was NOT programmed and the study MRI scan was NOT completed (e.g. Subject changed their mind about undergoing MRI scan, etc.)	
 • Document enrollment (name of the study, date of consent and inclusion/exclusion), MRI Scan Visit and study MRI scan information in the subject's medical and/or study records • Complete the Pre-MRI Scan Form • Note that the subject did not have the MRI Settings programmed on the pre-MRI CRF. • Complete deviation for inclusion/exclusion criteria not met • Complete the Withdrawal CRF. The patient is withdrawn.
If the MRI Pre-Scan Visit has taken place, the MRI Settings WERE programmed but the study MRI scan was NOT completed (e.g. Subject changed their mind about undergoing MRI scan, etc.)	
 • Document enrollment (name of the study, date of consent and inclusion/exclusion), MRI Scan Visit and study MRI scan information in the subject's medical and/or study records • Complete the Pre-MRI Scan Form • Complete deviation for inclusion/exclusion criteria not met • Complete the Withdrawal CRF. The patient is withdrawn.

8.4.6. Complete system explants

If the subject has the entire study ICD/ CRT-D system removed at any time during the study, and the subject will not receive a replacement study ICD/ CRT-D system, withdraw the subject from the study. Complete a Product Out of Service CRF and submit through EDC. A System Revision CRF is not required to be submitted.

8.4.7. System revisions

In cases where only the device pocket is revised (leads are not repositioned, leads have not been disconnected from the ICD/ CRT-D), a System Revision CRF is not required to be submitted. A System Revision CRF should be completed for all other types of revisions

such as generator replacement, lead replacement and lead repositioning has been performed.

8.4.7.1. Revisions before the MRI scan

A system revision is defined as a replacement of or repositioning of one or more components of the study ICD/ CRT-D system that occurs after the subject has been consented into the study. Because all components of the study ICD/ CRT-D system are market-released, all procedures related to the revision should be performed according to standard of care. The revision may be performed by either a study investigator or other clinician qualified to perform such procedures.

Any explanted devices or leads (including damaged leads, lead segments and lead fragments) should be returned to Abbott promptly for analysis. Document any change to the status of the lead and device (e.g. capped, removed) on the Product Out of Service CRF. Refer to **Table 4** to determine which case report forms need to be completed and submitted. Refer to **Table 8: System Revisions Scenarios Prior to MRI Scan** below to determine what actions need to be performed.

8.4.7.2. Revisions after the MRI scan

If a system revision occurs after the MRI scan, then the subject will remain in the study until the subject completes the 1 Month Post Scan visit.

Any explanted devices or leads (including damaged leads, lead segments and lead fragments) should be returned to Abbott promptly for analysis. Document any change to the status of the lead and device (e.g. capped, removed) on the Product Out of Service CRF. Refer to

Table 9: System Revisions Scenarios After MRI Scan below to determine what actions need to be performed.

TABLE 8: SYSTEM REVISIONS SCENARIOS PRIOR TO MRI SCAN

System Revisions that occur prior to MRI Scan	Action	Data Submission

Revisions where the study ICD/ CRT-D system is still implanted:
 
 • Study lead(s) or the ICD/ CRT-D is repositioned or replaced, AND • The study ICD/ CRT-D and study lead(s) are still implanted, AND • No other non-MRI compatible material has been implanted 	
Obtain (if possible):
 
 • In-clinic bipolar and unipolar* capture threshold at a pulse width of 0.5 ms. for the applicable lead(s). Either the manual decrement or automatic (in-clinic, programmer based) method may be used to obtain the capture threshold. • In-clinic bipolar sensing amplitude for the applicable lead(s). Either the incremental or the automatic (in-clinic, programmer based) method may be used to obtain the sensing threshold. • In clinic atrial and ventricular bipolar and unipolar* lead impedance for the applicable lead • Retain the subject in the study. If the MRI scan visit has not occurred yet, then wait at least 45 days from the successful revision before completing the MRI scan visit. If the MRI scan visit has occurred, then follow the subject through the 1 Month Post Scan visit. 
*NOTE: Unipolar and bipolar configurations should be collected for LV leads
	
Complete and submit the appropriate forms to Abbott. Refer to Table 4. It is recommended that the following device printouts and measurements be maintained at the site.
 
 • FastPath Summary • Test Results with Freezes, Include Battery & Leads • Wrap-up Overview with full parameters

Revisions where the study ICD/ CRT-D system is not retained, and the MRI Settings have not been programmed
	
The subject will be withdrawn from the study.
	
Document consenting information (name of the study, date of consent and inclusion/exclusion) in the subject's medical and/or study records.

System Revisions that occur prior to MRI Scan	Action	Data Submission

 • Study leads, or study ICD/ CRT-D was explanted but was not replaced with another study lead or study ICD/ CRT-D, and/or • A non-MRI compatible material(s) or device(s) was implanted 		
Submit the Screen Failure CRF. Submit Deviation or Product Out of Service CRFs if applicable. It is recommended that the following device printouts and measurements be maintained at the site.
 
 • FastPath Summary • Test Results with freezes, Include Battery & Leads • Wrap-up Overview with full parameters

Revisions where the study ICD/ CRT-D system is not retained, and the MRI Settings were programmed
 
Study leads, or study ICD/ CRT-D was explanted but was not replaced with another study lead or study ICD/ CRT-D, and/or
 
A non-MRI compatible material(s) or device(s) was implanted
	
The subject will be withdrawn from the study.
	
Document consenting information (name of the study, date of consent and inclusion/exclusion) in the subject's medical and/or study records.
 
Submit the Pre-MRI CRF, and Withdrawal CRF.
 
Submit Deviation or Product Out of Service CRFs if applicable.
 
It is recommended that the following device printouts and measurements be maintained at the site.
 
 • FastPath Summary • Test Results with freezes, Include Battery & Leads • Wrap-up Overview with full parameters

TABLE 9: SYSTEM REVISIONS SCENARIOS AFTER MRI SCAN

System Revisions that occur after the MRI Scan	Action	Data Submission

Revisions where the study ICD/ CRT-D system is still implanted
 
 The study ICD/ CRT-D and study lead(s) are still implanted, BUT A non-MRI compatible material(s) or device(s) has been implanted 
OR
 
Revisions where the study ICD/ CRT-D system is still implanted
 
 Study ICD/ CRT-D and study lead(s) is repositioned or replaced, AND The study ICD/ CRT-D and study lead(s) are still implanted, AND No other non-MRI compatible material has been implanted 	
Obtain (if possible):
 
 In-clinic bipolar and unipolar* capture threshold at a pulse width of 0.5 ms. for the applicable lead(s). Either the manual decrement or automatic (in-clinic, programmer based) method may be used to obtain the capture threshold. In-clinic bipolar sensing amplitude for the applicable lead(s). Either the incremental or the automatic (in-clinic, programmer based) method may be used to obtain the sensing threshold. In clinic bipolar and unipolar* lead pacing impedance for the applicable lead(s) Continue to follow the patient until the subject completes the 1 Month Post scan visit. 
*NOTE: Unipolar and bipolar configurations should be collected for LV leads
	Once required testing has been performed, complete and submit the appropriate forms to Abbott. Refer to Table 4

Revisions where the study lead(s) is not retained
 
 Study lead(s) is replaced with another lead, AND The study ICD/ CRT-D is still implanted, AND 	The subject will be withdrawn from the study.	
Document consenting information (name of the study, date of consent and inclusion/exclusion) in the subject's medical and/or study records.
 
Submit the Pre-MRI CRF, MRI CRF, System Revision CRF and Withdrawal CRF. Submit

System Revisions that occur after the MRI Scan	Action	Data Submission

 • A non-MRI compatible material(s) or device(s) has been implanted 		
Deviation, Product Out of Service, Adverse Event CRFs if applicable.
 
It is recommended that the following device printouts and measurements be maintained at the site.
 
 • FastPath Summary • Test Results with freezes, Include Battery & Leads • Wrap-up Overview with full parameters

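### Section 8.4.7.2 keeps every subject revised after the MRI scan to the 1-month visit, but one row of Table 9 withdraws some of them, and several post-scan revision types fit no row.

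*Combined protocol and SAP*

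**What the plan says.** **General rule.** Section 8.4.7.2 opens: "If a system revision occurs after the MRI scan, then the subject will remain in the study until the subject completes" the 1-month visit. It lists no exceptions and then refers the site to Table 9 for actions. Section 8.4.7.1 supplies the definition: "A system revision is defined as a replacement of or repositioning of one or more components of the study ICD/ CRT-D system", occurring after consent.

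**Table 9, first row.** This covers cases where the study generator and study leads are still implanted, with or without added non-MRI compatible material. Its action agrees with the general rule: "Continue to follow the patient until the subject completes the 1 Month Post scan visit".

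**Table 9, second row.** The heading is "Revisions where the study lead(s) is not retained". Its first condition is "Study lead(s) is replaced with another lead, AND", joined to two more: the study generator is still implanted, and a non-MRI compatible material or device has been implanted. The action is "The subject will be withdrawn from the study".

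**Complete explant.** Section 8.4.6 begins "If the subject has the entire study ICD/ CRT-D system removed at any time during the study" and, where no replacement study system will follow, withdraws the subject. It asks for no System Revision form.

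**What withdrawal means.** Under section 8.3.2, safety surveillance stops at withdrawal. Under section 14.6, nothing further is recorded except vital status, although the site should try to arrange a final visit with a device assessment. Under section 8.2.2, the effectiveness analysis uses subjects with complete data from pre-scan to 1 month.

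**The concern.** Before the scan there is a plain reason to withdraw a subject who no longer has an intact study system: section 8.4.4.3 makes that subject ineligible for the scan. After the scan that reason has gone, because the exposure under study has already taken place.

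A revision in the following month is also not a neutral event. Appendix A defines a complication as a serious adverse device effect that needs invasive intervention or leads to death, and the MRI-related window runs through the 1-month visit. Subjects who need a revision are therefore among those in whom the safety question is most active. If the site's reading of two conflicting instructions decides whether they are followed, loss to follow-up is linked to outcome, in groups that may hold as few as 10 scanned subjects.

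**Working it through.** The plan gives no figure to reproduce here, so the check sets the texts side by side and then shows the scale of one affected subject.

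**Step 1: is there a direct conflict?** Replacing a study lead is a system revision under section 8.4.7.1. A scanned subject who meets all three conditions of Table 9's second row is therefore covered by the opening sentence of section 8.4.7.2. That sentence retains the subject and the row withdraws the subject, so the two cannot both be followed. The first row retains a subject who receives non-MRI compatible material while the study system stays in place, so such material alone is not treated as grounds for withdrawal after the scan.

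**Step 2: does Table 9 cover every case?** Cross four lead states (kept; repositioned or replaced by a study lead; replaced by a non-study lead; removed and not replaced) with three generator states (kept; replaced by a study generator; non-study or removed) and with non-MRI compatible material absent or present. That gives 4 × 3 × 2 = 24 combinations, less the one in which nothing changed, which leaves 23. The first row is read generously, so that either the lead or the generator may have been changed.

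| Table 9 result | Combinations |
|---|---|
| First row, follow to 1 month | 7 |
| Second row, withdraw | 2 |
| No row: generator non-study or removed | 4 × 2 = 8 |
| No row: study generator, non-study lead, no added material | 2 |
| No row: study generator, lead removed and not replaced | 2 × 2 = 4 |

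So 8 + 2 + 4 = 14 of 23 match no row. Up to 4 of these (lead replaced by a non-study lead or removed, generator non-study or removed) could fall under section 8.4.6 if the whole study system has gone. These are counts of logical cases, not frequencies. Table 8, for revisions before the scan, does have rows for a component explanted and not replaced by a study component; Table 9 has no counterpart.

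**Step 3: scale of one affected subject.** Section 8.1.12 gives 15 enrolled per group, to secure 10.
- Share of a group: 1/15 = 6.7% to 1/10 = 10%.
- Share of the study: 1/60 = 1.7% to 1/(4 × 10) = 2.5%.
- Leads lost besides the one replaced. In a two-lead group (2 or 3), one other lead: 1/30 = 3.3% to 1/20 = 5% of the group's leads. In Group 4, with three leads, two others: 2/45 = 4.4% to 2/30 = 6.7%.

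**Step 4: illustration for effectiveness.** Assume one lead per subject, one subject revised, and every other lead a success. Exact Clopper-Pearson 95% limits are beta quantiles: the lower limit is B(0.025; x, n − x + 1) and the upper is B(0.975; x + 1, n − x), with upper limit 1 when x = n.

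| Scanned | Revised subject dropped | Kept and counted as a failure |
|---|---|---|
| 10 | 9/9 = 100% (66.4 to 100) | 9/10 = 90% (55.5 to 99.7) |
| 15 | 14/14 = 100% (76.8 to 100) | 14/15 = 93.3% (68.1 to 99.8) |

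The right-hand column needs a rule that a replaced lead counts as a failure. The readable text states no such rule, and the detail in SAP 2.3.2 is redacted. Retention alone would not produce it.

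**The case against.** The case on the other side is substantial, and most of it narrows the point.

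- **Withdrawal is not general.** From the row's heading, a reader might infer that Table 9 withdraws everyone whose study lead is not retained. It does not: all three conditions must hold. Replacement by another study lead falls in the first row.
- **The unmatched cases are not without a retention rule.** The opening sentence of section 8.4.7.2 still applies to replacements, and section 14.6 keeps every enrolled subject to the end of required follow-up. What these cases lack is an assigned set of tests and forms.
- **Section 8.4.6 may not conflict at all.** A reader might call it a flat contradiction. Explant without replacement is arguably not a revision as defined, and it has its own section. A clear conflict arises only if the whole system is replaced by a non-study system. It remains relevant because its wording also reaches subjects already scanned.
- **The triggering event is not lost.** A reader might infer that withdrawal removes the complication from the safety data. The second row calls for the System Revision and Withdrawal forms, and for an Adverse Event form where applicable. Section 16.1.2 requires reporting of adverse device effects within 24 hours. SAP 3.2 keeps withdrawn subjects in the adverse event denominator with their last known status. Section 14.6 asks for a final visit and, for withdrawals over device safety or performance, permission to follow the subject outside the study.

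The direct conflict in Step 1 is untouched by these arguments. Last known status cannot record a later event before 1 month, and nothing says that a final visit stands in for the 1-month measurement.

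**Conclusion.** The point holds in a limited form. One post-scan scenario receives two incompatible instructions within section 8.4.7.2. Table 9 leaves several other scenarios without assigned procedures. Section 8.4.6 raises a related question rather than a clear contradiction.

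The consequence is possible loss of later safety events before 1 month, and loss of the subject's remaining leads from the complete-data effectiveness analysis. Each affected subject is 6.7% to 10% of a group, on the assumption of 15 to 10 subjects. That is a share, not an effect estimate: the documents give no expected number of revisions in the 30 to 44 days after the scan, and it may be zero.

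The documents do not support a claim that the primary safety estimate is biased. The analysis populations in SAP 2.1 and the analysis detail in SAP 2.3.1 are redacted, so how withdrawn scanned subjects count there cannot be determined.

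**What to change.** Reconcile sections 8.4.6 and 8.4.7.2 and Table 9 so that a subject already scanned stays in study follow-up through the 1-month visit, in line with the existing opening sentence of section 8.4.7.2. That follow-up would collect safety data and measurements on any study lead still in place, and record measurements that are no longer possible as not applicable. Recast Table 9 so that each post-scan revision type falls in exactly one row, with its tests and forms.

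This matches choices made elsewhere in the protocol: section 8.4.4.5 keeps subjects who could not tolerate the scan and schedules their 1-month visit, and the first row of Table 8 follows a revised subject through 1 month if the scan visit has taken place.

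The cost is a change of protocol wording and one visit already scheduled for the few subjects affected. The change concerns study follow-up and data collection only. It says nothing about how a revision or explant should be managed clinically, and subjects keep their right to withdraw.
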